The application tracks the number of times the device is used in a day and time stamps those sessions. For each session, the application records the HRV data from the forehead sensor of the device and what frequency the auditory and visual stimuli the device emitted during the 15 minutes. Prior to and immediately after each session the application will ask users to rate the amount of pain they are feeling in the moment on a Visual Analog Scale (VAS) along a number line from "no pain" to "worst imaginable pain". The first time the device is used each day, participants will be asked to complete a VAS for how they slept from the night prior. For the last use of the device prior to going to sleep for the day, participants will only be asked to complete the VAS prior to using the device to not disrupt sleep patterns. Additionally, at the last use before sleep participants will be asked to select which of their medication for pain management they took that day. The medications will appear in a drop-down menu on the application. Medications will be reported by each individual to the research team at the first baseline visit week 0 and will be inputted by the research team into each participant's application. Every two weeks during the 8-week intervention period the application will also prompt users to complete the following additional questionnaires: the Neuropathic Pain Symptom Inventory, the Pittsburgh Sleep Quality Index and Patient Health Questionnaire Type 9 for Depression (PHQ-9) and the General Anxiety Disorder 7-item questionnaire (GAD-7). A reminder to complete these biweekly questionnaires will be sent to participant's cell phones via text message and on the tablets themselves. Additionally the application will send compliance messages to participants if participants do not fill out the fortnightly questionnaires.

- Between baseline visits (week 0 – 2) and between follow-up visits (week 10 -14) monitoring of pain at home – tablet only .

During these time periods participants will be asked to use the tablet with the application daily at night prior to sleep. Participants will be asked to complete a VAS of how they slept the night prior, a VAS of pain and asked to report the medications they used that day for pain management.

Description of Procedures Being Performed

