Devices: Participants will be instructed to use the Sana PR every time they experience pain during the day (ad libitum). There will be no minimum or maximum number of uses. Participants will open the Sana Health application and will be prompted to answer the amount of pain they are feeling in the moment using the VAS on the Sana Health application. If it is the first time the participant is using the device for the day, they will also be prompted by the application to complete a VAS to report on how they slept the evening prior. Participants will then turn on the devices using the application. Participants will complete a 15-min cycle with the device. Participants may complete multiple, sequential uses of the device without requiring them to interface with the application. Participants will be prompted to answer the amount of pain they are feeling in the moment after using the VAS on the Sana Health application.

Participants will also be asked to use the Sana PR device every evening immediately prior to/accompanying falling asleep for the night. Participants will open the Sana Health application and will be prompted to answer the amount of pain they are feeling in the moment using the VAS on the Sana Health application. Participants will then be prompted as to what medication they took for their pain that day. The application will be populated with the medications participants reported at the first baseline visit.

Participants will select from this list of medications. Participants will complete a 15 min cycle with the device.

Every two weeks during the 8-week intervention period participants will receive a message on their cellular devices via text message to complete the NPSI, PSQI, PHQ-9 and GAD-7. Participants will be sent compliance reminders to complete these questionnaires on their phones and on the tablet.

Safety monitoring: Participants will be instructed to contact the research team to report any AE over this period. Compliance will be monitored over the 8 week intervention period. A significant decrease in the compliance during (responding to less than 70% of the last 10 scheduled check-ins) of using the device the 8 week intervention will be considered an indication that a participant may need assistance. A research team member will call the participant to ensure that the reason of the drop in usage of the device is not due to an AE.

POST INTERVENTION FOLLOW UP (Week 10) - AT THE ARC OR VIA VIDEO CALL Participant

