Information will be collected including:

- Record of changes in medications
- Record of changes in pain management techniques participants typically used
- Documentation of the location of their pain on a body chart

Participants will then complete the following questionnaires:

- Neuropathic Pain Symptom Inventory (NPSI)
- Pittsburgh Sleep Quality Index (PSQI)
- Beck Depression Inventory (BDI)
- Patient health Questionnaire Type 9 for Depression (PHQ-9)
- General Anxiety Disorder 7-item questionnaire (GAD-7)
- World Health Organization Quality of Life Bref (WHOQOL-BREF) & World Health Organization Quality of Life Pain (WHOQOL-pain)
- Patient's Global Impression of Change (PGIC)
- Human Factors Questionnaire

- Responses to questions on ease of device use and the likelihood they would hypothetically continue using the devices in their daily life.

Devices: Participants will be asked to return the Sana PR mask at this visit. The application will stop working to control the device at the end of the 8-week intervention and will not let participants to continue using the Sana PR device.

Safety monitoring: Participants will be asked to report any AEs.

CONTINUED PAIN MONITORING BETWEEN FOLLOW UP VISITS (Week 10 – Week 14) - AT THE HOMES OF THE PARTICIPANTS

Participants will be asked to use the tablet with the Sana application daily, at night prior to going to sleep. Participants will be asked to complete a VAS of how they slept the night prior, a VAS of their amount of pain and asked to report the medications they used that day for pain management.

4 WEEK FOLLOW UP VISIT (WEEK 14) - AT THE ARC OR VIA VIDEO CALL Participant information will be collected including:

- Record of changes in medications
- Record of changes in pain management techniques participants typically used - Documentation of the location of their pain on a body chart

Participants will then complete the following questionnaires:

- Neuropathic Pain Symptom Inventory (NPSI)
- Pittsburgh Sleep Quality Index (PSQI)
- Beck Depression Inventory (BDI)
- Patient health Questionnaire Type 9 for Depression (PHQ-9)
- General Anxiety Disorder 7-item questionnaire (GAD-7)
- World Health Organization Quality of Life Bref (WHOQOL-BREF) & World Health Organization Quality of Life Pain (WHOQOL-pain)
- Patient's Global Impression of Change (PGIC)
- Human Factors Questionnaire

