We will use mixed modelling to determine the effect of the intervention on reported chronic pain – our primary outcome variable. We will also use ANOVAs (or their non-parametric equivalents) to assess changes in all of our outcome measures; including pain scores, sleep scores, device usage statistics, medication usage, heart rate variability, blood pressure, and quality of life measures.

6. Safety Assessment

Participants will be monitored for possible AEs throughout the study according to the frequency of the data review below. Participants will be given the email and phone number of the research team to report AE and circumstance of events. Participants will be reminded during the familiarization session with the device, at the second baseline visit, to seek immediate medical attention should they experience an injury as a result of being in the study. This will also be reiterated to participants if they reach out to report an AE. Data from the Sana Health application will be used to track compliance. Significant decrease in the compliance during (responding to less than 70% of the last 10 scheduled check-ins) of using the device the 8 week intervention will be considered an indication that a participant may need assistance. A research team member will call the participant to ensure that the reason of the drop in usage of the device is not due to an AE. Any AEs that occurs will be reported to the IRB to see if risk/benefit ratio is still acceptable for each individual participant and for the continuation of the study as a whole.

7. Benefits

Although no benefits can be guaranteed, it is possible that subject will experience a reduction in amount of chronic pain that they typically experience.

While there is no guarantee that this study will be beneficial to society, we hope that this study will help lead to the development of a device that can help reduce chronic pain and provide individuals who experience chronic pain with an alternative solution for managing pain.

8. Payment and Remuneration

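### Only pain gets a mixed model; the fortnightly sleep and mood scores (and pain again) go to ANOVA of change, whose usual forms discard interim scores when the analysed occasion is missed

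*Combined protocol and SAP*

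**What the plan says.** Section 5 (Data Analysis plan) is two sentences long. The first reads "We will use mixed modelling to determine the effect of the intervention on reported chronic pain – our primary outcome variable". The second reads "We will also use ANOVAs (or their non-parametric equivalents) to assess changes in all of our outcome measures; including pain scores", and its list continues with "sleep scores, device usage statistics, medication usage, heart rate variability, blood pressure, and quality of life measures". Pain therefore has two analyses, and no outcome other than pain is given a mixed model. Section 5 does not state the form of the ANOVA, the analysis population, or how withdrawals and missed occasions are handled.

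Section 4 (Study Procedures) sets the collection schedule. In weeks 2 to 10, every two weeks, "participants will receive a message on their cellular devices via text message to complete the NPSI, PSQI, PHQ-9 and GAD-7". The same four questionnaires are also completed at the visits in weeks 0, 2, 10 and 14. WHOQOL and BDI are completed only at those four visits, and PGIC only at weeks 10 and 14. Randomisation takes place at the week 2 visit.

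**The concern.** A participant who leaves in week 7 has already given week 4 and week 6 scores on NPSI, PSQI, PHQ-9 and GAD-7. A likelihood-based mixed model uses them. An ANOVA of week-10 change has no value for that person and omits them. An ordinary repeated-measures ANOVA or a Friedman test omits anyone who lacks a single required occasion.

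Two things are at stake. For sleep, depression and anxiety, the only planned result may be a completers' result although the data for a better one are held. For pain, two results may come from two different sets of people. If people who feel no benefit leave more readily in one arm, the completers' comparison is biased. The question is live here because the sham has earplugs, no sound and a plain light on/off cycle, so a difference between arms in why people leave cannot be excluded.

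**Working it through.** **1. What a mixed model could recover, by outcome** (schedule from Section 4, methods from Section 5; the fortnightly prompts are read as weeks 4, 6, 8 and 10)

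| Outcome | Named method | Occasions (weeks) | Post-randomisation scores held for someone leaving in week 7 |
|---|---|---|---|
| PSQI, PHQ-9, GAD-7 | ANOVA or rank test | 0, 2, 4, 6, 8, 10, 14 | weeks 4 and 6 |
| NPSI | ANOVA or rank test; also the mixed model if it is the primary pain scale | as above | weeks 4 and 6 |
| WHOQOL, BDI | ANOVA or rank test | 0, 2, 10, 14 | none |

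For the first two rows, usable data would be discarded. For the third, a mixed model adds something only for participants who have one of weeks 10 and 14.

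**2. The plan's own figure.** The enrolment goal is 180. No alpha, power, effect size, SD or dropout rate is given, so it cannot be reproduced. As a reference effect, assume 1:1 allocation (90 per arm), two-sided 5% and 80% power: (1.960 + 0.842) × √(2/90) = 0.418 SD.

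**3. Participants kept under random misses.** Assume each of the five post-randomisation occasions (weeks 4, 6, 8, 10, 14) is missed independently with probability p. Listwise deletion over all five keeps (1 − p)^5. A week-10 change analysis keeps 1 − p.

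| p | All five occasions | Week-10 change |
|---|---|---|
| 5% | 0.95^5 = 77% (139 of 180) | 95% (171) |
| 10% | 0.90^5 = 59% (106) | 90% (162) |
| 15% | 0.85^5 = 44% (80) | 85% (153) |

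If the same people miss repeatedly, more complete rows survive than the first column shows.

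**4. Bias and precision.** Simulation with 3000 trials per scenario, 90 per arm, unit SD, scores at weeks 2, 4, 6, 8 and 10, correlation 0.5 or 0.7 between scores four weeks apart, and an effect growing linearly to 0.418 SD at week 10. Dropout is permanent, can begin at week 6, and depends at most on the change from baseline to the previous score (so it is missing at random). Dropout was about 14–23% per arm. Each range covers the two correlations; effects are reductions in SD units.

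| Dropout pattern | Completers, change at week 10 | Likelihood, all scores |
|---|---|---|
| Unrelated to response | 0.415–0.417 | 0.414–0.417 |
| Driven by non-improvement alike in both arms | 0.394–0.401 | 0.417–0.421 |
| Driven by non-improvement in the sham arm only | 0.241–0.306 | 0.411–0.417 |
| Opposite directions in the two arms | 0.179–0.265 | 0.412–0.420 |

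As fractions of 0.418, completers recover 94–96% in the second row, 58–73% in the third and 43–63% in the fourth. With no true effect, the last two patterns gave completers a false difference of 0.12–0.23 SD in favour of sham, against about zero with all scores. Exchanging the arms' dropout patterns would reverse its sign.

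Precision when dropout is unrelated to response (about 19%): standard error 0.205 against 0.194 at correlation 0.5 (ratio 1.057) and 0.166 against 0.156 at 0.7 (ratio 1.064). With no true effect the ratios are 0.201/0.192 = 1.047 and 0.164/0.155 = 1.058. The precision loss is therefore about 5–6%.

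Adjusting the completers' analysis for baseline, in place of analysing change, reduces the bias without removing it: 0.323–0.340 for sham-only and 0.288–0.308 for opposite patterns.

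**The case against.** The strongest reply is that the primary outcome already has the right method. A reader might infer that nothing shows which pain analysis decides the trial. The text does not support that: Section 5 attaches the mixed model to the primary outcome variable and brings in ANOVA as an additional analysis. The natural reading makes the mixed model primary, and an explicit statement of precedence is all that is missing.

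Second, deletion is an inference. Section 5 does not say whether the ANOVA is of week-10 change, repeated-measures, or on per-person averages. The 77/59/44% figures hold only for listwise deletion over all five occasions and cannot be quoted against ANOVA in general.

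Third, a reader might infer that every outcome has fortnightly scores going to waste. WHOQOL and BDI do not. Device usage, medication and heart rate variability are recorded daily or per session and could be summarised per person.

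Fourth, nothing in the documents shows that incomplete data will be common. There are reminders, calls when compliance falls, video visits, and $100 of the $150 payment tied to the two follow-up visits. Daytime use is as needed with no minimum, so someone who stops using the mask can still complete week 10.

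All four stand as limits on scope and size. They do not remove the core: for the fortnightly sleep and mood questionnaires the only named methods are ones whose usual forms ignore scores the trial will hold, and no missing-data rule prevents this.

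**Conclusion.** The point holds for PSQI, PHQ-9 and GAD-7, for NPSI to the extent that it is not the primary pain scale, and for the second analysis of pain. It should be corrected, but it does not undermine the planned primary analysis.

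Its size is unknown in advance. It runs from no bias and a 5–6% larger standard error, through a 4–6% loss of effect when response drives dropout alike in both arms, to roughly 27–57% lost when dropout depends on response differently by arm. A reader might take the upper end as the expected result. The documents give no dropout rate or pattern, so those figures are adverse scenarios under assumed correlations, 1:1 allocation and about 14–23% dropout per arm. The likelihood analysis stays close to the truth here because the simulated dropout was missing at random; it would not be protected otherwise.

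**What to change.** In Section 5:

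- State that the mixed model is the deciding analysis of pain. Label any ANOVA or rank test of pain scores supportive and completers-only.
- Analyse NPSI, PSQI, PHQ-9 and GAD-7 with the same likelihood-based mixed model: everyone randomised, every observed occasion, with an arm-by-visit term.
- Allow the same model for WHOQOL and BDI, noting that it helps only participants who have one of weeks 10 and 14. Keep simple tests for outcomes analysed at a single occasion.
- Add a sensitivity analysis for data missing not at random (for example, shifting unobserved scores by arm over a stated range), and keep a rank-based check for skewed outcomes.

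This is a wording change plus a little programming with a model type the plan already uses, and it needs no new data or participants. The price is reliance on missing-at-random and approximate normality, which the last item is there to examine.
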